- h. We will also recruit from each cohort's group of 12 study participants, two influential agents of change (AoC), who will be identified as being the most respected by other study participants. These study participants will be identified using data collected

during the pre-intervention interview. Specifically, during the interview, study participants will be asked to identify people they know in the community. Then for each person they indicate knowing, they will be asked how much they respect that person on a 5-point Likert scale. The two most respected persons in each cohort will be invited via telephone to be a member of their cohort's Advisory Committee. If either of the two persons declines the invitation, the 3rd most respected person will invite and so on until at least two agree to participate in this role. During the Advisory Committee recruitment call, the role of being a committee member will be described (i.e., attend three committee meetings and remind other participants to attend intervention activities and events).

- i. Informed consent will be obtained prior to participation in the screening interview. Screening interviews will be conducted in-person at the housing community and also by telephone. If the screening interview is conducted by phone, we will obtain verbal consent. The date that verbal consent is provided to participate will be noted on a copy of the informed consent document by the interviewer along with the participant's name. Following the screening interview, the dated copy will be stored with the study records and a blank copy will be mailed to the participant to keep for their records. If the screening interview is conducted in-person, prior to beginning the interview the interviewer will go over the informed consent document with the participant. The participant will then be asked to sign the form if they consent to participate in the screening interview. The signed copy will be kept and stored with the study records, and the participant will be given an unsigned copy for their records.

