- p. Eligible participants will complete a 30-minute pre-program (baseline) interview over the phone. They will be asked will be asked questions about things they do, physical activities they engage in, their social relationships with other residents in the community, and their health.
- q. Pre-program interviews will be administered through Qualtrics, and participants will be asked whether they know each of the other members of their intervention cohort. For each person they indicate knowing, they will be asked how much they respect that person on a 5-point Likert scale. The two most respected persons in each cohort will be invited via telephone to be a member of their respective cohorts' Advisory Committee. If either of the two persons declines the invitation, the 3rd most respected person will be invited. This will continue until two people agree to serve on the committee. During the Advisory Committee member recruitment call,

the role of being a committee member will be described (i.e., attend three committee meetings and remind other participants to attend intervention activities). Advisory Committee members will be asked to remind other cohort members to attend intervention activities only by making note of intervention activities during their regular interactions with the other participants (e.g., when see them in the hallway or in community common areas). They will not be asked to go out of their way to do this.

- r. Participants will be asked to wear a physical activity monitoring device (i.e., ActivPAL) on their thigh for 7 consecutive days after their pre- and post-program interviews. This is a small device that would be placed on your thigh with the help of a gentle adhesive. This device will continuously monitor their physical activity including activities like sitting, standing, walking and/or running. It will be recording the energy they had spent while performing the above-mentioned activities. When we retrieve this device from them, we will be looking at a number of values that tell us about their physical activity levels such as time spent sitting, standing, number of steps taken while walking and/or running, as well as energy spent per day.

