### III. Statistical design

- a. Sample size: Two sequential cohorts of 12 residents living in a HUD subsidized independent-living senior housing community in Ypsilanti, MI will be recruited for participation in this study. Both cohorts will receive the same intervention. The size of each cohort is capped at 12 to facilitate participation among all participants during group components of the intervention. A sample size of 24 was estimated to be sufficient in order to reach data saturation from quantitative process measures and theoretical saturation of themes from qualitative (i.e., open-ended) evaluation data (see Aim #2 below).
- b. AIM 1) Identify agents of change (AoC) and implement intervention. Within two sequential cohorts of 12 residents living in a HUD subsidized independent-living senior housing community, AoC will be identified.
  - i. Data analysis plan: Within each group of 12 study participants AoC will be identified using data collected during the pre-intervention interview. Specifically, during the interview, study participants will be asked to identify people they know in the community. Next, social network analysis will be conducted using these data with Ucinet. AoC will be identified as the top two study participants in their cohort on the social network measure of in-degree centrality (i.e., number of other study participants who report knowing them).
  - ii. Power analysis: A power analysis was not conducted for the proposed analysis due to the descriptive nature of the social network analyses.

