components from the post-intervention interviews will begin with an open-coding process to develop a codebook. This will involve the PI and Graduate Student Research Assistants (GSRAs) working on the program. Each person will read the text responses and independently develop a list of themes in the data. Next the team will meet to discuss the themes with a goal of reaching consensus on the list of themes and develop and agreed upon definition for each theme. This information will then be compiled into a codebook containing the list of themes/codes and their definition. Following this, the GSRAs will conduct axial coding. This will include associating specific passages of text with the themes/codes developed during the open-coding process. This will be done using qualitative data analysis software (NVivo). Inter-rater reliability (kappa) will be calculated for an initial sample of text passages coded by the GSRAs. If discrepancies exist, they will be discussed and the process repeated until kappa  $>0.80$ .

3. Power analysis: A power analysis was not conducted for the proposed analysis due to the descriptive nature of the proposed analyses, including analysis of open-ended text responses and descriptive analysis of process outcomes across the entire sample of study participants.
- d. AIM 3) Examine changes in secondary outcomes and differences in process and secondary outcomes by whether knew an AoC at baseline.
  - i. Hypotheses: The following hypotheses based on Social Contagion Theory and the Convoy Model of Social Relations will be tested: H3a-Network influence: Residents knowing 1+ committee members at baseline will participate in more intervention activities compared to those who do not. H3b-Pain as modifier: The network influence on participation will be greater among residents reporting more pain at baseline compared to those reporting less pain.
  - ii. Data analysis plan: Analysis for aim 3 will begin with descriptive analysis of secondary outcomes (physical function, PA, and pain) measured via self-report during both the pre- and post-intervention interviews. This will be done using statistical software (e.g., SPSS) and will include examination of variable frequencies, measures of central tendency, and sample variation. Next change scores will be created to document change in these measures from pre- to post-intervention and descriptive analyses conducted on these variables.

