- e. Analysis of accelerometry data: This study will use an accelerometer (activPAL) to measure physical activity among study participants. The activPAL is worn on the thigh continuously for 7-days. It has been shown to reliably measure sedentary time (including lying and sitting time) and activity intensity (i.e., estimates of energy expenditure) (Lyden et al., 2018). Raw data from the activPAL will be exported using activPAL provided software to a .csv file. The data will then be processed using an R-

package developed by developed specifically for activPAL data (Lyden et al, 2018). The data will be processed at the second level (1-second epochs). The same R-package will then be used to sum the following over the 7-day period I which the device was worn: 1) sedentary (i.e. sitting/lying) time (i.e., number of 1-second epochs of <1.50 metabolic equivalents); 2) light activity (i.e., standing and stepping) time (i.e., number of 1-second epochs between 1.50 and 2.99); and 3) moderate or higher activity time (i.e., number of 1-second epochs 3.00 or higher). The above data preparation and analysis steps will be applied to both the pre- and post-intervention accelerometry data. As a final step we will create changes scores in each of the three objectively measured indicators of activity (sedentary, light, and moderate or higher). Following creation of these variables, descriptive analysis will be conducted on these variable including examination of frequencies, measures of central tendency, and sample variation.

- f. Hypothesis testing: To test the proposed hypotheses (i.e., to test the presence of social network influence), mean differences and corresponding 95% confidence intervals in process measures (e.g., number of intervention activities that study participants participated in) and changes in secondary outcomes described above will be compared between study participants who knew one or more AoC at baseline and those who did not. Next, within these two groups we will stratify by pain measures to explore descriptively whether pain moderates network influence on outcomes.
- g. Power analysis: A power analysis was not conducted for this pilot study given the proposed small non-representative sample, which is likely to produce inaccurate estimates of effect size and their corresponding standard errors.

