- h. Reference: Lyden, K., Keadle, S. K., Staudemayer, J., & Freedson, P. S. (2017). The activPAL™ accurately classifies activity intensity categories in healthy adults. *Medicine and science in sports and exercise*, 49(5), 1022-1028.

\*\*\*\*Ame00151969\*\*\* Included with this amendment is the change that we were not able to collect data from two sequential cohorts within the same HUD subsidized independent-living senior housing community ([Community Name]). We will now be recruiting the second cohort at a second HUD subsidized independent-living senior housing community ([Community Name]) in Ann Arbor, MI. The study intervention remains the same

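### The test of network influence (H3a) has no cohort term although the two cohorts live in different communities, so a community difference can pass for, or hide, agent-of-change influence

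*Combined protocol and SAP*

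**What the plan says.** H3a, in section III.d.i, is directional: "Residents knowing 1+ committee members at baseline will participate in more intervention activities compared to those who do not". Section III.f gives the analysis: "To test the proposed hypotheses (i.e., to test the presence of social network influence), mean differences and corresponding 95% confidence intervals in process measures", together with changes in the secondary outcomes, "will be compared between study participants who knew one or more AoC at baseline and those who did not". The only further split is by pain: "within these two groups we will stratify by pain measures to explore descriptively whether pain moderates network influence on outcomes". Neither III.f nor any other section names cohort or community as a covariate, a stratum or a sensitivity analysis.

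The amendment repeated at the end of sections II and III changes the setting: "We will now be recruiting the second cohort at a second HUD subsidized independent-living senior housing community". It states that the intervention is unchanged and leaves III.f as it was.

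Exposure is tied to the cohort. Section III.b.i says that "AoC will be identified as the top two study participants in their cohort". The tie question is worded in two ways. II.q says that "participants will be asked whether they know each of the other members of their intervention cohort", whereas II.h (and similarly III.b.i and V.d) says that "study participants will be asked to identify people they know in the community". Under either wording the AoCs are chosen within a cohort, so a participant is exposed to the AoCs of his or her own cohort. III.f does not say whether the AoCs themselves enter the comparison.

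**The concern.** Cohort, community and calendar period now coincide. The share of participants who know an AoC depends on how well connected each cohort is. Attendance can also differ by cohort for reasons unrelated to ties: 4 of the 10 activities are group sessions (II.v), and their day and time are discussed with each cohort's own Advisory Committee (II.t). If the better-connected cohort also attends more, the pooled difference is positive with no AoC influence at all. If it attends less, a real influence can be masked.

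The plan reads this difference as evidence for or against network influence, which is the substance of Aim 3. The same comparison is applied to changes in the secondary outcomes.

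**Working it through.** **Inputs from the documents.** Two cohorts of 12, with two AoCs each, leave 12 − 2 = 10 non-AoC participants per cohort. The outcome is the number of activities attended out of 1 + 4 + 4 + 1 = 10 (II.u to II.x). H2c sets a mean of 7. No SD, exposed share, attendance gap or power figure is given for H3a, so there is no planned figure to reproduce.

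**Assumptions.** SD 2 activities, no true AoC effect, and a gap in mean attendance between communities of 1 or 2 activities. Exposed counts e1 and e2 (of 10 each) are varied.

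**Bias of the pooled difference.** It equals the gap times the difference in cohort mix between the two groups:

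bias = gap × [e1/(e1 + e2) − (10 − e1)/(20 − e1 − e2)]

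- 8 v 6: 8/14 − 2/6 = 0.24 per activity of gap, so 0.24 at gap 1 and 0.48 at gap 2.
- 9 v 4: 9/13 − 1/7 = 0.55, so 0.55 and 1.10.
- Equal counts, or a gap of 0, give exactly 0.

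**Simulation.** 20,000 trials per cell; attendance normal with mean 7, cohort means at plus and minus half the gap, rounded and clipped to 0–10; least squares with t intervals. Clipping makes the simulated bias slightly smaller than the formula.

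| Exposed, of 10 each | Formula bias, gap 1 / 2 | Simulated crude bias, gap 1 / 2 | Crude 95% CI above 0, gap 1 / 2 (nominal 2.5%) |
|---|---|---|---|
| 7 v 6 | 0.11 / 0.22 | 0.10 / 0.20 | 3.1% / 2.6% |
| 8 v 6 | 0.24 / 0.48 | 0.22 / 0.44 | 3.9% / 4.7% |
| 9 v 4 | 0.55 / 1.10 | 0.50 / 1.02 | 7.5% / 15.6% |
| 10 v 4 | 0.71 / 1.43 | 0.68 / 1.33 | 10.3% / 24.4% |
| 9 v 2 | 0.71 / 1.41 | 0.65 / 1.32 | 10.5% / 27.2% |
| 10 v 2 | 0.83 / 1.67 | 0.77 / 1.54 | 13.3% / 37.5% |

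At 8 v 6 the total error stays near 5% (3.9 + 1.0 = 4.9% at gap 1, 4.7 + 0.4 = 5.1% at gap 2), but it moves to one side. At 7 v 6 it is 3.1 + 1.5 = 4.6% and 2.6 + 0.8 = 3.4%. With the gap reversed at 9 v 4 (gap −2) the bias is −1.0, and the interval lies below zero in 14.7% of trials.

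Keeping all 12 per cohort tells the same story. At 9 v 6 exposed the bias is 0.27 (gap 1) and 0.53 (gap 2); at 9 v 3 it is 0.50 and 1.00.

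**With a cohort term.** The bias from community is about 0 and each tail about 1% to 3% (9 v 4, gap 2: bias 0.00, 2.9% above and 2.7% below).

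**Price in precision.** The within-cohort standard error is SD/√(sum over cohorts of e(10 − e)/10). At 9 v 4 this is 2/√(0.9 + 2.4) = 1.10, against a crude 2 × √(1/13 + 1/7) = 0.94. Simulated half-widths with no gap, crude then adjusted:

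- 8 v 6: 1.94 and 1.99
- 9 v 4: 1.86 and 2.19
- 10 v 4: 1.94 and 2.57
- 9 v 2: 1.78 and 2.52
- 10 v 2: 1.81 and 3.15

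With a gap of 2, the adjusted interval is narrower at 8 v 6 (1.94 against 2.13) and wider at 9 v 4 (2.14 against 1.99).

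**AoCs kept in.** Suppose all 12 per cohort are analysed, the four AoCs are coded as exposed, and they attend 1 or 2 more activities than others (assumption). The cohort-adjusted bias is then 0.20 or 0.38 at 8 v 6, and 0.26 or 0.51 at 9 v 4, with no community gap.

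**The case against.** The strongest reply is that the harm is hypothetical and the remedy not clearly better. Both conditions are needed, and the documents establish neither. At 7 v 6 and 8 v 6 the bias of 0.1 to 0.4 is small beside a half-width of about 1.9 to 2.1. If both communities had one common chance of 0.5 to 0.8 of knowing an AoC, with independence between participants (assumption), counts would differ by 5 or more in only about 1% to 4% of studies.

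At a gap of 1, adjustment brings no gain in root mean squared error: 0.96 v 0.96 at 8 v 6, 1.03 crude v 1.06 adjusted at 9 v 4, and 1.17 v 1.55 at 10 v 2. The benefit appears at a gap of 2 (1.36 v 1.05 at 9 v 4; 1.77 v 1.55 at 10 v 2), which is a full assumed SD. The study is also a 24-person pilot with no decision rule on H3a, and III.g already warns that effect sizes will be inaccurate. Nor does a cohort term touch the confounding inside each cohort, where more sociable residents may both know an AoC and attend more.

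Most of this stands, and it limits the severity. It does not remove the point. Under the same common-chance assumption, counts differ by 2 or more in 39% to 50% of studies, and real differences between communities would add to that. The III.g caveat concerns a small, unrepresentative sample; it does not mention community, and a warning about imprecision does not cover a bias with a direction. The error trade-off is a reason to show both estimates. The current plan gives the reader no way to see whether they disagree.

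**Conclusion.** The concern holds as a conditional one. The planned H3a contrast is confounded with community whenever exposed share and attendance both differ between cohorts, and the plan neither adjusts for this nor reports what is needed to detect it. Under the assumptions above, the spurious difference is 0.1 to 0.4 activities at mild imbalance, 0.5 to 1.0 at 9 v 4, and 0.7 to 1.5 at the extreme splits, in either direction. The true size is unknown, because the documents give no exposed shares, SD or attendance gap.

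Severity is low to moderate. The change should be made because it is cheap, but it does not threaten the feasibility aims. Whether the AoCs are in the contrast is a separate gap of similar size (0.2 to 0.5 activities under its own assumption).

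**What to change.** In section III.f:

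- Estimate the difference between knowing one or more AoCs and knowing none within cohort, and combine: a linear model of activities attended on exposure and cohort, with a 95% confidence interval. Do the same for the secondary-outcome change contrasts.
- State that the AoCs themselves are left out of this contrast.
- Show the crude difference beside the adjusted one, and report exposed and unexposed counts and mean attendance by cohort.
- If everyone, or no one, in a cohort knows an AoC, say that this cohort adds nothing to the adjusted contrast.
- Describe the result as an association, since sociability remains a confounder within each cohort.

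The cost is SAP wording; cohort and ties are already collected. The statistical price is one degree of freedom and, with no community gap, an interval wider by 1% at 7 v 6, 3% at 8 v 6, 18% at 9 v 4 and 74% at 10 v 2. Because the adjusted estimate can have the larger overall error when the gap is small, the crude figure should stay in the report.

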### b. Specific Aims

- i. List of Specific Aims
  1. Identify agents of change (AoC) and implement intervention.
  2. Evaluate feasibility of intervention implementation.
  3. Examine changes in secondary outcomes and differences in process and secondary outcomes by whether knew an AoC at baseline.
- ii. The following process hypotheses will be tested: At least 75% (3 of 4) of identified AoCs will accept the invitation to serve on Advisory Committee; AoC will attend at least 2 of 3 committee meetings; Participants will on average participate in at least 70% (7 of 10) of intervention activities; Residents knowing 1+ committee members at baseline will participate in more intervention activities compared to those who do not; The network influence on participation will be greater among residents reporting more pain at baseline compared to those reporting less pain.

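### H3b (pain as modifier) is listed as a hypothesis to be tested, but III.f only describes pain strata and gives no estimate or interval for the moderation contrast.

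*Combined protocol and SAP*

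**What the plan says.** I.b.ii introduces a list that includes the pain-modifier statement with "The following process hypotheses will be tested". III.d.i repeats it under Aim 3, saying that the hypotheses "based on Social Contagion Theory and the Convoy Model of Social Relations will be tested", and words it as "H3b-Pain as modifier: The network influence on participation will be greater among residents reporting more pain at baseline compared to those reporting less pain".

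III.f, headed as hypothesis testing, provides "mean differences and corresponding 95% confidence intervals in process measures" and in changes in secondary outcomes, compared "between study participants who knew one or more AoC at baseline and those who did not". That serves H3a. For pain, it adds only that "within these two groups we will stratify by pain measures to explore descriptively whether pain moderates network influence on outcomes".

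III.f does not name the pain measure, say that it is the baseline one, give a cut-point, or say what pattern would count for or against H3b. It does not say whether the AoCs themselves belong to the group that knew an AoC. III.a justifies the sample by saturation ("A sample size of 24 was estimated to be sufficient in order to reach data saturation"), and III.g states that no power analysis was done.

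**The concern.** H3b is a statement about one quantity: the knew-minus-did-not-know difference in participation at higher pain, minus the same difference at lower pain. Describing four cells does not estimate that quantity or show how uncertain it is. A reader who has been told that H3b will be tested would then see four means and judge by eye whether the pattern runs the right way. In a sample of 24 split four ways, sizeable patterns appear by chance, and nothing in III.f would flag them. H3a does not have this problem, because its comparison carries an interval.

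**Working it through.** **Inputs from the documents.** N = 2 × 12 = 24 (III.a). This is the plan's only design figure; it rests on saturation, so there is no power or precision figure to reproduce. The outcome is the number of activities attended, from 0 to 10: one first individual meeting, four group sessions, four brief check-ins and one final meeting (II.u to II.x), 1 + 4 + 4 + 1 = 10, which matches the 7-of-10 target in H2c.

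**Assumptions.** The documents give no SD, group split or pain cut-point. I take SD = 2.5 activities (range 2 to 3) and a median split on pain, with each knowledge group halved by pain for the precision figures.

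**Precision of the contrast.** SE = SD × √(1/n₁ + 1/n₂ + 1/n₃ + 1/n₄); half-width = t(0.975, 20) × SE, where t = 2.086 and df = 24 − 4.

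- Equal cells: √(4/6) = 0.82, so 2.086 × 0.82 = 1.70 SD, and 1.70 × 2.5 = 4.3.
- Cells 9/9/3/3: √(2/9 + 2/3) = 0.94, giving 1.97 SD, or 4.9.
- Cells 10/10/2/2: √(2/10 + 2/2) = 1.10, giving 2.29 SD, or 5.7.

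**Chance patterns.** With no true moderation the contrast falls in the H3b direction half the time. The chance that it reaches +2 or more is 1 − Φ(2 / SE). For equal cells, SE = 2.5 × 0.82 = 2.04 and 1 − Φ(0.98) = 16%.

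| Knew / did not know | Half-width, SD 2 | SD 2.5 | SD 3 | Chance of +1 or more (SD 2.5) | Chance of +2 or more (SD 2.5) |
|---|---|---|---|---|---|
| 12 / 12 | 3.4 | 4.3 | 5.1 | 31% | 16% |
| 18 / 6 | 3.9 | 4.9 | 5.9 | 34% | 20% |
| 20 / 4 | 4.6 | 5.7 | 6.9 | 36% | 23% |

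If the four AoCs are left out (N = 20, df = 16), equal cells give 1.90 SD, or 4.7 activities at SD 2.5.

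**Sparse cells, if non-knowers are few.** With 12 of 24 above the median on pain, the number of non-knowers with higher pain is hypergeometric. For 4 non-knowers, the chance that one of their pain cells holds at most one person is 1 − C(12,2)² / C(24,4) = 1 − 4,356 / 10,626 = 59%; the chance of an empty cell is 2 × 495 / 10,626 = 9%. For 6 non-knowers the chance of a cell with at most one person is 16%.

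**How many non-knowers to expect.** The documents do not say. A simulation of the in-degree rule in III.b.i (two cohorts of 12, independent ties) gives mean counts, among the 20 non-AoC participants, of 11.8, 7.9, 5.2, 3.2 and 1.8 who know neither AoC, at tie densities of 0.1, 0.2, 0.3, 0.4 and 0.5. The split may be roughly even or very uneven, depending on a density nobody has stated.

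**The case against.** The strongest reply is that III.f already treats H3b as exploratory. Its wording on pain is descriptive, its reference to testing is explained in brackets as the presence of network influence (which is H3a), and III.g warns that estimates and standard errors from this sample are likely to be inaccurate. The protocol also uses testing loosely elsewhere: III.c says that H2a to H2c will be tested and gives them descriptive analysis only. This stands, and it makes the defect a mismatch between sections plus a missing estimate. A reader might infer a disguised confirmatory test; the text does not support that, and no section says a cell pattern will be declared to support H3b.

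A reader might also infer that the two groups are bound to be very uneven because AoCs are the best-known residents. The documents give no split. They also conflict on the rule: III.b.i selects by number of participants who know the person, while II.h, II.q and V.d select by respect. Unevenness would make matters worse, but the point does not need it.

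Nor is it right that the plan reports no spread at all. Its descriptive analyses elsewhere include sample variation, which may carry over to the strata. That is still not an interval for the contrast.

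Finally, the fix does not let the trial answer H3b. Power for a moderation effect of 1 SD at a two-sided 5% level is 21% with a 12/12 split and 14% with 20/4. That is a reason to show the interval, not to omit it.

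**Conclusion.** The point holds as a mismatch and an omission. Two sections promise a test of H3b. The analysis section describes strata and never estimates the difference of differences, while giving H3a an interval in the same paragraph. Even in the most favourable layout, four equal cells, the 95% half-width is about 4.3 activities (3.4 to 5.1 for SD 2 to 3), and a chance contrast of +2 or more occurs in about 16% of studies, rising to 23% with 4 non-knowers (both at SD 2.5). These sizes rest on the assumed SD and a pain split into halves. The sparse-cell figures hold only if non-knowers are few, which the documents neither state nor rule out. The feasibility aim is not affected.

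**What to change.** In III.f, pre-state one H3b contrast for total activities attended: (knew minus did not know) at higher baseline pain, minus the same at lower baseline pain. Report it with its 95% confidence interval and the four cell counts, and state that it is not estimable if a cell is empty. Name the baseline pain measure and the cut-point in advance, and say whether the AoCs are counted. In I.b.ii and III.d.i, relabel H3b as exploratory so that those sections agree with III.f.

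A model with a knew-an-AoC by continuous baseline pain term and cohort as covariate is an optional supporting analysis. It avoids a cut-point, but it is unstable when only 3 or 4 participants know no AoC: in simulations its interval was wider than that of the split in roughly 34% to 44% of samples, with a much worse upper tail.

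The cost is a change of wording and one extra estimate from data already collected. The downside is that the interval will be wide and will show that this pilot cannot confirm H3b.
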